**Table 9–1 Flow chart**

Visit number	Baseline (Visit 1)	Assessment visits (Visit 2.1, 2.2, 2.3, , )	End of study (Visit 3)
Visit window 		0 - 99 EDs	$\geq 100^2$ EDs
PATIENT RELATED INFO / ASSESSMENTS			
Informed consent	●		

Visit number	Baseline (Visit 1)	Assessment visits (Visit 2.1, 2.2, 2.3, , )	End of study (Visit 3)
Visit window		0 - 99 EDs	≥100  EDs
Consent to report FVIII genotype result	●		
Inclusion/Exclusion Criteria	●		
Withdrawal Criteria	●	●	●
Haemophilia treatment history	●		
Concomitant illnesses	●		
Medical history	●		
Concomitant medication	●	●	●
Demography	●		
Body measurements	●	●	●
FVIII genotype	● 	● 	● 
Details of haemophilia	●		
Family history of haemophilia	●		
EFFICACY			
Bleed(s)		●	●
Surgery	●	●	●
SAFETY			
Adverse reactions	●	●	●

Visit number	Baseline (Visit 1)	Assessment visits (Visit 2.1, 2.2, 2.3, , )	End of study (Visit 3)
Visit window		0 - 99 EDs	≥100  EDs
Physical examination	●	●	●
Vital signs	●	●	●
FVIII recovery	●	●	●
FVIII trough level	●	●	●
FVIII inhibitors	● 	● 	● 
OTHER ASSESSMENTS			
HIV status	● 		
T cells subset: CD4+	● 		
STUDY MATERIAL			
Administration of turoctocog alfa	●	●	●
Diary dispensing and/or collection	●	●	●
Review of patient Diary data		●	●
End of Study form			●

For patients with on-demand treatment, the time period between visits is recommended not to exceed 6 months

100 EDs with turoctocog alfa after inclusion in the study

In this non-interventional study, only results from assessments performed according to local clinical practice will be recorded. However, adverse reactions (ARs) should always be assessed and reported

An available genotype result will be documented if consented to by the patient/LAR

If a genotype test is performed during the study, the result will be documented, if consented to by the patient/LAR.

A 48 hours washout period is recommended

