#### **9.3.1 Visit procedures**

Patients will obtain routine medical care at their respective clinic in accordance with local practices. All study visits should be performed according to local clinical practice. No additional visits should be conducted due to the participation in this study.

At each visit the Physician should provide information as specified in the below sections, if available. The Physician must keep a patient enrolment log and a log of patients evaluated for, but not included in the study throughout the enrolment period. These logs can be combined in one document. Patient identification is to be accomplished via allocation of a six digit number which consists of a three digit site code and a three digit patient ID. Numbers will be provided by Novo Nordisk.

Signed informed consent must be obtained prior to any study related activities.

Patients enrolled in the study will be provided with contact address(es) and telephone number(s) of the Physician site and/or staff. During a patient's participation in the study, all relevant data should be entered in the pCRF. In case a patient is being prematurely withdrawn from the study the Physician will ensure that the procedures for the last visit are recorded, if possible. The primary reason (e.g. adverse drug reaction or other) for discontinuation must be specified in the pCRF.

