**9.3.1.3 End of study visit (Visit 3)**

This visit will take place when the individual patient or at least 50 patients in the study have reached a minimum of 100 EDs after inclusion in the study whichever comes first. The visits should be

scheduled according to local clinical practice and should if possible also be performed for withdrawals.

When Novo Nordisk has confirmed that a total number of 50 patients in the study have reached a minimum of 100 EDs, the sites must contact on-going patients and request that all patient diaries are returned to the site, and ask for any safety information since last visit. The contact can be performed during a regular site visit or a phone contact. To finalise the study documentation the data should be recorded in the pCRF not later than 8 weeks from the announcement that 50 patients have reached 100 EDs within the study.

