### **9.3.3.5 FVIII inhibitor testing**

Blood sampling for inhibitor detection can be performed according to local clinical practice. As described in the EMA guideline, the Physician is encouraged to test for FVIII inhibitors according to [Table 9-2](#), preferably at least 48 hours after last treatment. If the patient is already being treated with turoctocog alfa at inclusion, the result of the inhibitor sample taken prior to initiated treatment

with turoctocog alfa must be available and negative. After inclusion in the study Novo Nordisk offer to provide analysis for FVIII inhibitors at a Central Laboratory selected by Novo Nordisk.

A positive inhibitor test is defined as  $\geq 0.6$  BU for central laboratory analyses, or above the specific local laboratory reference range. A patient has a confirmed inhibitor if the patient has been tested positive for inhibitors at two consecutive tests preferably within two weeks.

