### **9.7.3 Primary endpoint**

The incidence rate of inhibitors ( $\geq 0.6$  BU for central laboratory analyses, or above the specific local laboratory reference range) represented as the percentage of patients developing inhibitors will be calculated and a 1-sided 97.5% upper confidence limit will be provided based on an exact calculation for a binomial distribution. For the calculation of the incidence rate the numerator will include all patients with inhibitors confirmed by laboratory except those patients who have received a positive inhibitor test result after inclusion in the study for a test performed prior to first dose of turoctocog alfa. The denominator will include all patients in the trial exposed to turoctocog alfa,

except those patients who have received a positive inhibitor test result after inclusion in the study for a test performed prior to first dose of turoctocog alfa, these patients will be listed separately.

In addition, the time to inhibitor development will be presented by Kaplan Meier plot. Furthermore, an annualised rate of inhibitors per patient year will be calculated using a Poisson model allowing for over-dispersion with a log-link function and the logarithm of the time spent in the trial as offset, if appropriate.

Analyses and presentations will be made for each treatment regimen (preventive treatment or on-demand treatment) and for all patients, and furthermore for each patient subgroup (Severity of Haemophilia A: severe, moderately severe or patients with surgery/invasive procedure).

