### **9.7.5 Evaluability of patients for analysis**

All main descriptions and analyses of safety and efficacy data will be based on the Full Analysis Set, as defined in ICH E9 Guidelines (Statistical Principles for Clinical Trials). The Full Analysis Set includes all dosed patients with data after dosing, except those patients who has had received a positive inhibitor test result after inclusion in the study for a test performed prior to first dose of turoctocog alfa, these patients will be listed separately.

No formal Per-Protocol analysis is planned. However, the sensibility of the results with respect to single patient's data may be investigated by performing additional analyses on subsets of data.

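### The primary inhibitor percentage divides by all exposed patients although no inhibitor test after first dose is compulsory, so untested patients count as inhibitor-free

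*Protocol*

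**What the plan says.** Protocol section 9.7.3 sets both parts of the primary percentage. For the top, "the numerator will include all patients with inhibitors confirmed by laboratory". For the bottom, "The denominator will include all patients in the trial exposed to turoctocog alfa". One group is removed from both: patients whose positive result became known after inclusion but came from a sample taken before first dose. An exact binomial 1-sided 97.5% upper limit goes with the percentage.

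Confirmation is defined in section 9.3.3.5: "A patient has a confirmed inhibitor if the patient has been tested positive for inhibitors at two consecutive tests preferably within two weeks".

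Testing after first dose is left to the site:

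- Section 9.3.3.5: "Blood sampling for inhibitor detection can be performed according to local clinical practice". The schedule in Table 9–2 (0, 10–15, 50–75 and about 100 exposure days, EDs) is a recommendation.
- Table 9–1, note 3: "only results from assessments performed according to local clinical practice will be recorded".
- Section 9.3.1: "No additional visits should be conducted due to the participation in this study".
- Section 9.3.1.3, for patients still ongoing when the 50th patient reaches 100 EDs: "The contact can be performed during a regular site visit or a phone contact".

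The only compulsory inhibitor test is the negative one before first dose (section 9.2.2, criterion 5). The general analysis set in section 9.7.5 does not require a later one: "The Full Analysis Set includes all dosed patients with data after dosing".

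**The concern.** An exposed patient with no inhibitor test after first dose cannot meet the two-positive rule, but is still counted in the denominator. Such a patient is treated as observed and negative. Missing tests can remove patients from the numerator, never from the denominator, so the error has one direction. The confirmation rule adds to it, because the repeat sample is also only recommended and a single unrepeated positive counts as no inhibitor.

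The Protocol handles another optional endpoint the opposite way. In section 9.7.4, missing haemostatic responses are left out because reporting them is optional. Section 9.9 concedes that assessments are not mandatory, but no rule in section 9.7.3 follows from that.

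At stake is the single primary safety result. Section 7.2 cites about 3 inhibitors per 1000 patient-years in previously treated patients, so zero or one case is a realistic outcome. With zero cases the upper limit carries the information, and it then depends only on the denominator.

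The supporting Poisson rate in section 9.7.3 has the same weakness. Its offset is time spent in the trial, which credits time during which no inhibitor could have been detected.

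**Working it through.** **Inputs.** Exposed patients: 70 (section 9.2.1, planned number included). Interval: exact binomial, 1-sided 97.5% (section 9.7.3). The untested share is not in the Protocol; 10% to 50% is an assumption, shown beside the case of full testing. The Protocol states no precision figure for the primary endpoint, so there is nothing of its own to reproduce.

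**Step 1: upper limit.** With x inhibitors among n patients, the limit is the 0.975 quantile of Beta(x+1, n−x). For x = 0 it is 1 − 0.025^(1/n). For n = 70: 1 − 0.025^(1/70) = 5.13%.

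**Step 2: compare denominators, 70 exposed.**

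| Untested after first dose | Tested n | Limit, 0 inhibitors | Percentage (limit), 1 inhibitor |
|---|---|---|---|
| 0% (same as planned rule) | 70 | 5.13% | 1.43% (7.70%) |
| 10% | 63 | 5.69% | 1.59% (8.53%) |
| 20% | 56 | 6.38% | 1.79% (9.55%) |
| 30% | 49 | 7.25% | 2.04% (10.85%) |
| 50% | 35 | 10.00% | 2.86% (14.92%) |

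The planned rule reports the first row whatever the true testing share. With 50 exposed and no inhibitors, the planned limit is 7.11%, against 8.81%, 10.00% and 13.72% at 20%, 30% and 50% untested.

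**Step 3: bias in the percentage.** If a share t is tested independently of inhibitor status and the true risk is p, the planned percentage estimates p × t. At p = 6% it estimates 4.8% for t = 0.8 and 3.0% for t = 0.5. With zero inhibitors observed, the percentage is 0 under either denominator and only the limit moves.

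**Step 4: coverage.** The smallest value the planned limit can take with n = 70 is 5.13%. It therefore covers every true risk up to 5.13%, whatever the testing share. Above that it can fail. At p = 6% it misses only when no inhibitor is found (with one, the limit is 7.70%), so coverage is 1 − (1 − 0.06t)^70:

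- t = 1: 98.7%
- t = 0.8: 96.8%
- t = 0.7: 95.0%
- t = 0.5: 88.1%

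**The case against.** The strongest reply is that the effect may be small. The Protocol encourages testing at set exposure days, on lack of effect and on clinical suspicion. It offers central analysis with kits supplied, and asks for two tests around surgery if available. If 10% to 20% are untested, the limit moves only from 5.13% to 5.69–6.38%. This stands: the size is unknown and may be nil. A reader might take the roughly 50 expected completers of 100 EDs as the number tested, but the Protocol does not link the two. Patients who stop early can be tested at 10–15 or 50–75 EDs.

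A second reply also stands. Because testing is partly prompted by symptoms, untested patients may be at lower risk, and a tested-only percentage may be too high. Neither denominator is free of bias, which is why both should be shown.

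Some stronger readings are tempting but not supported:

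- That the limit generally lacks its 97.5% coverage. Step 4 shows this needs a true risk above about 5%. Even seven years at the cited 3 per 1000 patient-years is 7 × 0.003 = 2.1%.
- That patients may never have been tested at all. Inclusion criterion 5 requires a negative test before first dose; the gap concerns tests after it.
- That the Kaplan-Meier plot is wrong as written. Section 9.7.3 gives no censoring rule for it, and that detail may properly sit in the statistical analysis plan.
- That section 9.7.5 creates a materially conflicting denominator. It applies the same exclusion and differs only by dosed patients with no later data.

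The study is descriptive and tests no hypothesis. That lowers the consequence, but does not make an untested patient a negative one.

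**Conclusion.** The concern holds. The denominator is a rule that the Protocol itself fixes, not a detail left to a later document. It makes the percentage too low whenever an inhibitor occurs and some patients go untested after first dose. It also makes the upper limit too favourable for the number actually assessed. With 70 exposed and no inhibitors, the understatement runs from nothing (all tested) through about 0.6 percentage points (10% untested), 1.2 (20%) and 2.1 (30%) to 4.9 (50%). These sizes rest on the 70 in section 9.2.1 and on assumed untested shares. The figures for bias and coverage also assume that testing is unrelated to inhibitor status.

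**What to change.** In section 9.7.3:

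1. Calculate the percentage and exact upper limit among exposed patients with at least one valid inhibitor test after first dose, keeping the present exclusion of positives from before first dose.
2. Show the all-exposed percentage and limit beside it, and state that symptom-prompted testing may make the tested-only figure too high.
3. Tabulate the number of patients tested in each exposure-day window of Table 9–2. One early test is enough to enter the new denominator, so this table is needed to make patients tested only early visible.
4. In the Poisson model, replace time spent in the trial as the offset with time to the last valid inhibitor test, and state that the Kaplan-Meier plot is censored at the same point.

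The cost is a short change of text, slightly more analysis work and a somewhat less favourable upper limit. No extra samples, visits or data are needed.

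### The primary inhibitor percentage divides by all exposed patients although post-dose testing is optional, so any patient never tested counts as inhibitor-free and the upper limit may be too low

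*Protocol*

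**What the plan says.** Protocol section 9.7.3 fixes both parts of the primary percentage. On the numerator: "the numerator will include all patients with inhibitors confirmed by laboratory". On the denominator: "The denominator will include all patients in the trial exposed to turoctocog alfa". From both it removes patients whose pre-first-dose sample later proves positive. For precision, "a 1-sided 97.5% upper confidence limit will be provided based on an exact calculation for a binomial distribution".

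Section 9.3.3.5 sets the confirmation rule: "A patient has a confirmed inhibitor if the patient has been tested positive for inhibitors at two consecutive tests preferably within two weeks".

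The same section leaves testing to the site: "Blood sampling for inhibitor detection can be performed according to local clinical practice". The schedule in Table 9–2 is a recommendation. A footnote to Table 9–1 adds that "only results from assessments performed according to local clinical practice will be recorded", with adverse reactions as the exception. Sections 9.3.1.2 and 9.3.1.3 ask for inhibitor results only where they exist, and section 9.3.1 rules out extra visits for the study. Under section 9.3.1.3, patients still on study when the fiftieth patient reaches 100 exposure days may be closed out by telephone.

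Section 9.7.5 defines the analysis set: "The Full Analysis Set includes all dosed patients with data after dosing". It does not ask for an inhibitor result.

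**The concern.** A patient without a post-dose inhibitor test can never satisfy the two-positive-tests rule, yet adds one full unit to the denominator. An outcome that was not looked for is then reported as absent, on the endpoint that the study exists to measure. From the all-exposed figure alone, a reader cannot tell 0 cases among 70 tested patients from 0 cases among 49 tested patients.

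The protocol handles a lesser endpoint differently. In section 9.7.4, missing haemostatic ratings are left out because reporting them is optional. Inhibitor testing is just as optional, but section 9.7.3 has no corresponding rule.

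The denominator matters because few cases are expected. Section 7.2 gives a background rate of about 3 per 1000 patient-years. If 70 patients contributed one year each (an assumption), 70 × 0.003 = 0.21 cases would be expected. Zero or one case is the likely result, and the upper limit then depends almost wholly on the number in the denominator.

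**Working it through.** **Inputs.** About 70 patients included and about 50 completing (section 9.2.1); exact one-sided 97.5% limit (section 9.7.3). The share *t* of exposed patients with at least one post-dose test is not in the protocol, so it is assumed and varied. The protocol states no expected limit or precision, so there is no planned figure to reproduce.

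**Formula.** With *x* cases among *n* patients, the limit is the 0.975 quantile of a beta distribution with parameters *x* + 1 and *n* − *x*. For *x* = 0 this is U = 1 − 0.025^(1/*n*).

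**70 exposed.**

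| Share tested | Patients tested | Limit, 0 cases | Limit, 1 case |
|---|---|---|---|
| 100% (same as all-exposed) | 70 | 5.13% | 7.70% |
| 90% | 63 | 5.69% | 8.53% |
| 80% | 56 | 6.38% | 9.55% |
| 70% | 49 | 7.25% | 10.85% |

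With 50 exposed and no case, the limit is 7.11% as written, 7.87% with 45 tested and 8.81% with 40 tested.

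**Dependence on the risk of untested patients.** Let their risk be *r* times that of tested patients. The risk across all exposed patients is then the tested-patient risk × [*t* + (1 − *t*)*r*]. Take *t* = 0.8 and no case:

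- *r* = 1: 6.38%.
- *r* = 0.5: 6.38% × 0.9 = 5.74%.
- *r* = 0: 6.38% × 0.8 = 5.10%, practically the 5.13% obtained as written.

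For *r* between 0 and 1, the tested-only limit is therefore the upper end of the possible correction.

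**Coverage, 70 exposed, untested patients at equal risk.** The chance that a patient is detected is *q* = true risk × *t*. Coverage is the binomial probability of a case count whose all-exposed limit reaches the true risk.

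- True risk up to 5.13%: even 0/70 gives a limit of 5.13%, so coverage is 100% whatever the untested share.
- True risk exactly 5.13%, seen as the chance of finding no case: (1 − 0.0513)^70 = 2.5% if all are tested; with exponents 63, 56 and 49 it is 3.6%, 5.2% and 7.6%. Just above this risk, finding no case becomes a coverage failure.
- True risk 6.8%, 80% tested: at least one case is needed, and coverage is 98.0%, still above nominal.
- True risk 10%: 2/70 gives a limit of 9.94%, so at least three cases are needed. Coverage is 97.6% if all are tested, 92.6% at 80% and 79.9% at 60%.

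**Supplementary analyses.** The Poisson rate in section 9.7.3 uses time in the trial as its offset, whether or not the patient was tested, so it does not cure the problem. A patient with one positive test and no confirmatory sample also counts as inhibitor-free. Changing the denominator does not address that case.

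**The case against.** **The untested share may be small.** The protocol promotes testing at clinic visits and on lack of effect (section 9.1.1), on clinical suspicion and at set exposure-day intervals (section 9.3.3.5), and around surgery (section 9.3.1.2). It offers central analysis and supplies kits (sections 9.3.3.5 and 9.3.3.9). A never-tested patient has to miss all of this. At 10% untested the limit moves by 5.69 − 5.13 = 0.56 percentage points, and with full testing nothing changes. This stands, and makes the point conditional. It does not remove it, because none of the testing is mandatory and close-out may be by telephone.

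**Untested patients may carry less risk.** Testing is directed at suspected cases, so a tested-only percentage can err high. This also stands. It is a reason to show both figures, not to show only the all-exposed one.

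**The restriction is a low bar.** Patients may already be on turoctocog alfa at inclusion (section 9.1.1), so a Visit 1 sample could qualify them, and one early test is not complete ascertainment. That is correct: the change removes the clearest gap only.

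**A reader might infer that the limit has lost its 97.5% confidence in general.** The figures do not support that. With 70 exposed the limit cannot fall below 5.13%. The background rate corresponds to 0.3% over one year and 7 × 0.3% = 2.1% even over the full seven-year study, and coverage at such risks is 100%.

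**Nothing is decided on the limit.** Section 9.7.1 plans no hypothesis test, and the protocol sets no threshold for the limit. Section 9.9 acknowledges that assessments are not mandatory. This lowers the severity, but section 9.9 carries no remedy into the primary analysis.

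**Conclusion.** The point holds in conditional form. The protocol itself fixes a denominator that counts never-tested patients as inhibitor-free, so this is not a detail left to the SAP. If such patients exist, the percentage and upper limit are too low to the extent that those patients carry risk. For 70 exposed and no case, the limit of 5.13% would rise to at most 5.69%, 6.38% or 7.25% with 10%, 20% or 30% untested. Those shares are assumed, and the figures take untested patients to have the same risk as tested ones.

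The documents do not support saying outright that the limit is too low, because they do not show that anyone will go untested. Undercoverage can arise only at true risks above about 5%, and not at every such risk. This should be fixed, but it is not critical to the study's validity.

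**What to change.** In section 9.7.3, calculate the percentage and its exact limit among exposed patients with at least one FVIII inhibitor result from a sample drawn after the first turoctocog alfa dose, keeping the existing pre-dose exclusion. Present the all-exposed percentage and limit beside it. Report the number of patients never tested after dosing, and list them.

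This adds no test, visit or burden on patients. Section 9.6.2 already has sites mark tests not done on the case report form, which should help to identify these patients. The cost is about one sentence in the plan and an extra table line and listing. The limit becomes slightly less favourable, and the tested-only figure may err high where symptoms prompted the test, which is why both are shown.
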